After a subject has decided to enroll in the OLS, s/he will have up to 21 days to complete the screening procedures and enroll in the OLS. After 21 days, subjects who have NOT completed the screening procedures will be considered a screen failure. To be reconsidered for enrollment to the OLS, the subject will be required to repeat all screening procedures to reconfirm eligibility for enrollment in the OLS. These criteria also apply to subjects who missed the 7-day decision-making window to enroll in the OLS.

A written informed consent must be obtained from all subjects participating in the OLS before any trial-related procedures (including any screening procedures) are performed.

Eligible subjects who completed participation in Study Protocol 1720302 may be eligible for the first treatment (Baseline Treatment in Treatment Cycle 1 of OLS) during their EOS Visit window, but treatment may not be administered on the same day as the EOS Visit due to unavailability of screening safety laboratory results. In this case, the EOS Visit procedures and laboratory results from Study Protocol 1720302 will serve as the baseline data for this trial.

This study will also recruit new BoNT treatment-naïve or -experienced adult subjects, who were not enrolled in Study Protocol 1720302.

[REDACTED]

[REDACTED]

[REDACTED]

- [REDACTED]

- [REDACTED]

[REDACTED]

- [REDACTED]

- [REDACTED]

[REDACTED]

[REDACTED]

[REDACTED]

[REDACTED]

Two weeks after the Baseline/Treatment Study Visit (Day 1), study site staff will call the subject to inquire about CD symptom status and adverse events (AEs). The subject will return for protocol-specified assessments at Weeks 4, 6, 12, and every 4 weeks thereafter, up to Week 52 or EOS Visit.

Primary endpoints are safety and immunogenicity after multiple continuous treatment cycles of DAXI for injection. [REDACTED]

[REDACTED]

[REDACTED]

[REDACTED]

[REDACTED]

[REDACTED]

[REDACTED]

A subject may not be re-enrolled in the OLS after the EOS Visit (or after early discontinuation).

Study Visits and Telephone Calls:

- Screening (Days -21 to -1)
- Treatment #1, #2, #3, and #4
- Follow-up telephone calls after each Treatment:
 - Week 2 after each treatment (study site staff will call the subject)
- Follow-up visits after each Treatment:
 - Follow-up visits at Weeks 4, 6, 12, and every 4 weeks thereafter until the EOS Visit (52 weeks after Treatment #1 [Study Baseline]) (See Figure 1 Figure 1 and Table 1).

Safety Evaluations:

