7.2 SUBJECT DISCONTINUATION/WITHDRAWAL FROM THE STUDY

Subjects are free to withdraw from participation in the study at any time with notification.

An investigator may discontinue or withdraw a participant from the study for the following reasons:

- Pregnancy
- Significant study intervention non-compliance (e.g., failure to follow study procedures or to keep follow-up appointments)
- If any clinical AE, laboratory abnormality, or other medical condition or situation occurs such that continued participation in the study would not be in the best interest of the subject
- The subject experiences no reduction or have an increase in the average TWSTRS-total score at Weeks 4 and 6 post-injection relative to the pre-injection TWSTRS-Total score at the beginning of the treatment cycle (i.e., **lack of efficacy**: no improvement or worsened disease status)
- If the investigator determines that another BoNT treatment is needed to control the CD symptoms and less than 12 weeks have elapsed since the last study treatment administration
- If the subject meets an exclusion criterion (either newly developed or not previously recognized) that precludes further study participation

If the subject withdraws consent and discontinues from the study, the investigator will record the reason for consent withdrawal, if one is provided by the subject, in the subject's study records and on the eCRF. If a subject withdraws consent because of an AE, that AE should be indicated as the reason for withdrawal. In the event of early discontinuation, the subject should be asked to return to the study center to complete the assessments specified in the EOS Visit.

If at any time during the study, the investigator determines that it is not in the best interest of the subject to continue, the subject will be discontinued from participation. The investigator can discontinue a subject at any time if medically necessary. Appropriate documentation in the subject's study record and eCRF

regarding the reason for discontinuation must be completed. Prior to discontinuing a subject from study participation, the investigator will discuss his/her intentions with the medical monitor or designee.

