9.6 PLANNED ANALYSES

All efficacy endpoints, including responder rates, will be summarized with descriptive statistics by dose and/or treatment cycle, unless otherwise specified.

Discontinuation rate will be summarized by dose and cycle as well as overall. Additionally, the number of weeks on study will be summarized with descriptive statistics.

Duration of effect after each treatment, defined as time (number of weeks) from treatment until loss of 80% of the peak treatment effect (i.e., the average of the change from baseline in the TWSTRS-total score at Weeks 4 and 6)

[figure not shown]
- If a subject has no reduction in the TWSTRS-total score at Week 4 and Week 6, his/her duration of effect will be set to 0. If a subject discontinues or withdraws from the study prior or at Week 6, his/her duration of effect will be set to 0.
- If a subject discontinues or withdraws from the study prior to reaching his/her target TWSTRS score at any visit after Week 6, his/her duration of effect will be censored at the last visit. If a subject rolled over from Study Protocol 1720302 at Week 36 prior to reaching his/her target TWSTRS score, his/her duration will be calculated from the injection date in Study Protocol 1720302 to the time his/her TWSTRS-total score reaches/exceeds the target TWSTRS score.

Kaplan-Meier survival curves will be plotted for each dose level for the time-to-event endpoints. Point estimate of median duration and 2-sided, 95% confidence intervals (CIs), will be generated using the log-rank test. A subject might be counted more than once or in multiple groups due to multiple injections cycle. Exploratory statistical comparisons between subgroups and duration of response evaluation may be performed.

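### Protocol 9.6 gives a duration of effect of 0 to a subject who leaves at Week 6 with a documented response still present, against its own endpoint definition and its next censoring rule

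*Protocol*

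**What the plan says.** Protocol 9.6 measures duration of effect after each treatment as "time (number of weeks) from treatment until loss of 80% of the peak treatment effect", where the peak is the average change in TWSTRS-total at Weeks 4 and 6. Three rules follow.

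- Non-response: the rule opens "If a subject has no reduction in the TWSTRS-total score at Week 4 and Week 6" and assigns a duration of 0.
- Early exit, in the same bullet: "If a subject discontinues or withdraws from the study prior or at Week 6, his/her duration of effect will be set to 0". No condition on reason or on recorded scores is attached.
- Exit after Week 6 before the target score is reached, in the next bullet: "his/her duration of effect will be censored at the last visit".

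On the analysis, the section says "Kaplan-Meier survival curves will be plotted for each dose level for the time-to-event endpoints", with a median and two-sided 95% confidence interval. Exploratory subgroup comparisons may be added.

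The synopsis schedules "Follow-up visits at Weeks 4, 6, 12, and every 4 weeks thereafter", so two post-injection scores can exist by Week 6. Section 7.2 says "Subjects are free to withdraw from participation in the study at any time with notification". It also lists reasons for investigator withdrawal. Some are tied to efficacy (no reduction in the Week 4/6 average; another BoNT treatment needed within 12 weeks) and some are not (missed appointments, adverse events).

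The SAP's duration definition is blacked out in the public copy. Its section 10 drops the ITT and PP populations and multiple imputation, and the readable part does not mention the early-exit rule.

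**The concern.** A Week 6 leaver with both scores recorded and an average reduction is not a case of missing information. The peak is known, the target follows from it, and the subject has been seen not to have reached it. Entering 0 replaces a known lower bound of about 6 weeks with immediate loss of effect.

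A share of subjects placed at time 0 lowers the whole Kaplan-Meier curve for that dose level. If early exits differ between dose levels or cycles, for example through adverse events, part of an apparent difference in duration would come from the exit rule. No readable analysis would show this: the sensitivity analyses in SAP 8.3 cover TWSTRS-total, CGIC and PGIC by visit mode and COVID-19 impact, not duration.

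**Working it through.** The readable documents give no duration, early-exit rate or power figure for this endpoint, so there is no planned figure to reproduce. The check has a logical part and an illustration.

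**1. Does the rule contradict the definition?** Let B be the pre-injection score and W4, W6 the scores at Weeks 4 and 6.

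- Peak reduction: P = B − (W4 + W6)/2.
- Loss of 80% of the peak leaves 1 − 0.80 = 0.20 of it, so the implied target is T = B − 0.20 × P.
- If P > 0 and W6 < T, effect is present at Week 6 and duration exceeds about 6 weeks (the visit window is ±3 days).

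| Subject with P > 0, target not reached | Value under 9.6 | Value implied by the definition |
|---|---|---|
| Leaves at Week 6 | 0 | more than about 6 weeks, end unknown |
| Leaves at Week 12 | censored at last visit | more than about 12 weeks, end unknown |
| Leaves before Week 6 | 0 | P not defined (W6 missing) |

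The contradiction is in the first row only. In the third row there is no complete peak for the definition to act on.

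Reading 0 as an event at time 0 is an inference, but a strong one, because the adjacent bullet uses censoring when censoring is meant. Reaching the end of the study does not trigger the rule: Protocol 8.1.3 bars injections after Week 40, which leaves 52 − 40 = 12 weeks of follow-up.

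**2. How far could the median move?** If a share p is set to 0 and the others follow S0(t), then S(t) = (1 − p) × S0(t), and the reported median solves S0(t) = 0.5/(1 − p).

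Assumptions, none from the documents: Weibull S0 with shape 2; true median m of 20 or 24 weeks; all early exits unrelated to efficacy, so that censoring them would return S0. Then scale = m/√(ln 2) and t = scale × √(−ln[0.5/(1 − p)]).

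Example, m = 20 and p = 0.05: scale = 20/0.8326 = 24.02; 0.5/0.95 = 0.5263; −ln(0.5263) = 0.6419; √0.6419 = 0.8012; t = 24.02 × 0.8012 = 19.2 weeks.

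| p set to 0 | True median 20 | True median 24 |
|---|---|---|
| 2% | 19.7 (−0.3) | 23.6 (−0.4) |
| 5% | 19.2 (−0.8) | 23.1 (−0.9) |
| 10% | 18.4 (−1.6) | 22.1 (−1.9) |

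Over shapes 1 to 3 and true medians of 16, 20 and 24 weeks, the fall is 0.1 to 0.3 weeks at 1%, 0.2 to 0.7 at 2%, 0.4 to 1.8 at 5% and 0.9 to 3.6 at 10%.

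**3. Check with events detected only at visits.** A simulation used n = 350, 300 runs, shape 2 and true median 20, comparing set-to-0 with censoring at Week 4. The proportion event-free past Week 12 was 0.741 against 0.779 at p = 5%, and 0.702 against 0.781 at p = 10%. This agrees with the factor (1 − p): 0.95 × 0.779 = 0.740. Mean medians were 20.7 against 22.1 weeks at 5% and 20.1 against 22.0 at 10%. These gaps exceed those in the table partly because the assumed true median falls on the Week 20 visit, so a small drop in the curve can move the estimate by a whole visit interval.

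**The case against.** A reader might infer that the rule wrongly turns every early withdrawal into a treatment failure. The documents do not support that. Before Week 6 the two-visit peak is incomplete, so the definition yields no target, and 0 is a prespecified worst-case value. Some Week 6 exits are true failures, since sections 7.2 and 8.1.2.4 allow discontinuation on the Week 4/6 average. The rule also catches a case that the non-response sentence, read literally, could miss: a small gain at Week 4 outweighed by worsening at Week 6. These arguments stand, and they confine the point to Week 6 leavers with an average reduction and an unreached target.

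A second argument is that censoring every other early leaver would bias the result the other way. Subjects may leave because another BoNT treatment is needed (7.2, 8.1.2.4) or because rescue medication for CD is required (6.5.1), and their effect has probably gone. This also stands, and the fix treats those exits as loss of effect.

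A reader might also infer that the trial's main conclusions are at risk, or that the drug is flattered. Neither follows. The primary endpoints are safety and immunogenicity, efficacy is summarised descriptively, and the overall bias runs against the drug. Investigators select the dose (9.7.3), so dose comparisons are confounded in any case. Discontinuation is reported by dose and cycle (9.6) and reasons by cycle (SAP 7.1), so an imbalance would be visible. Visibility does not correct the curves, though, and conservatism overall does not protect comparisons between doses or cycles.

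**Conclusion.** The point holds in a narrow form. For a subject with an average Week 4/6 reduction who leaves at Week 6 short of the target, Protocol 9.6 as written produces a value that contradicts its own definition and the adjacent censoring rule.

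The size is unknown because no early-exit rate is given. Under the stated assumptions, the median falls by about 0.3 to 0.4 weeks at 2% set to 0 and by 1.6 to 1.9 weeks at 10%. The latter is also the gap that 0% against 10% early exits would create between two dose levels with the same true duration. Treat these as upper illustrations: they count all early leavers as unrelated to efficacy, whereas the affected group is smaller. At 1% to 2% the shift stays under a week across the whole range examined.

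Whether the SAP kept the rule cannot be checked, so no claim is made about the SAP's own derivation. The issue deserves correction because the recorded value is wrong for identifiable subjects and the repair is small.

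**What to change.** In Protocol 9.6, and wherever the SAP carries the rule over:

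1. Keep 0 when the Week 4/6 average shows no reduction, or when the recorded exit reason is lack of efficacy.
2. For an exit because another BoNT treatment or rescue medication for CD is needed, count loss of effect at the exit visit. State whether this also applies after Week 6, where the next bullet now censors; otherwise the inconsistency moves to a new place.
3. Censor other Week 6 leavers with a documented reduction and an unreached target at their last TWSTRS visit.
4. For exits before Week 6, 0 may stay as the stated worst-case convention. Add a sensitivity analysis that censors subjects with a Week 4 reduction who left for reasons unrelated to efficacy.
5. Report the present all-zero rule as a labelled worst case.

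The cost is a few lines of text, a small change to one derivation that uses the recorded withdrawal reason, and two further summaries. The main estimate becomes slightly less conservative, and the labelled worst case shows by how much.

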6.5.1 RESCUE MEDICINE

Rescue medication for CD is not allowed in this trial. Subject(s) may withdraw from the study at any time if rescue medication for CD is required.

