8.1.2.4 END-OF-STUDY VISIT

The EOS Visit for each subject in the OLS may occur when the subject:

- Prematurely withdraws from the study for specific reasons (e.g., AEs, pregnancy, or withdraws consent)
- Has no improvement or worsened disease status (i.e., lack of efficacy) after a treatment (consistent with no change or increase from baseline in the average of the TWSTRS-total score at Weeks 4 and 6 post-treatment)
- Requires another treatment less than 12 weeks from the last injection
- Reaches Week 52

Refer to the SOA (Table 1) for EOS activities.

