8.1.3 VARIATION FROM SCHEDULED VISIT DAYS

To allow for scheduling flexibility, limited variation will be permitted from the specified time of each visit (Table 3).

Table 3. Allowed Variation from Scheduled Visit Days

Scheduled Visit After Each Treatment	Allowed Variation (calendar days)
Weeks 4 and 6	± 3 days
Weeks 12, 16, 20, 24, 28, 32, 36, 40, 44, 48, and 52/EOS	± 6 days
Treatment #2, #3, and #4	± 14 days

Note: Two weeks after each Treatment (at Week 2 [allowed variation: ± 3 days]), the subject will be contacted by telephone to follow up on clinical effect, any AEs or changes in concomitant medications.

A subject who experiences significant recurrence of CD symptoms (e.g. pain) during the study before his/her TWSTRS-total score reaches the target TWSTRS score may request another treatment before the next scheduled visit. In this case, the subject may have an unscheduled visit for the investigator to assess whether another treatment is warranted based on the subject's symptoms and neurologic exam findings. If the investigator confirms that retreatment is clinically indicated, the subject may receive another treatment at this visit, unless less than 12 weeks have passed since the last injection or the injection will occur after Week 40 (i.e., there is less than 12 weeks of follow up left in the 52-week study period).

Note: After each Treatment, study visits are reset to begin from that Treatment to Week 4, Week 6, Week 12, and every 4 weeks thereafter.

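### Duration of effect: subjects who withdraw after Week 6 because benefit has worn off are censored, probably informatively, and the legible text gives no rule for cycles ended by retreatment before the TWSTRS target

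*Protocol*

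**What the plan says.** Protocol 9.6 defines duration of effect for each treatment as "time (number of weeks) from treatment until loss of 80% of the peak treatment effect", that is, until the TWSTRS total reaches the subject's target score. Kaplan-Meier curves and medians are planned by dose level. The special cases are:

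- Non-response: "If a subject has no reduction in the TWSTRS-total score at Week 4 and Week 6, his/her duration of effect will be set to 0".
- Early withdrawal: "If a subject discontinues or withdraws from the study prior or at Week 6, his/her duration of effect will be set to 0".
- Later withdrawal before target: for a subject who leaves "at any visit after Week 6, his/her duration of effect will be censored at the last visit". No distinction is made by reason.
- Week-36 rollovers from Study 1720302: time runs from the injection in that study to the target crossing. No other ending is named.

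Elsewhere the protocol describes three ways in which a cycle can end before target because benefit has gone:

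1. Toxin needed too soon. Section 7.2 lists as a ground for withdrawal: "If the investigator determines that another BoNT treatment is needed to control the CD symptoms and less than 12 weeks have elapsed". Section 8.1.2.4 has the matching end-of-study trigger: "Requires another treatment less than 12 weeks from the last injection".
2. Rescue needed. Section 6.5.1 does not allow rescue and adds: "Subject(s) may withdraw from the study at any time if rescue medication for CD is required".
3. Retreatment on request. Under 8.1.3, a subject with significant recurrence "before his/her TWSTRS-total score reaches the target TWSTRS score may request another treatment before the next scheduled visit". If the investigator confirms the need, and at least 12 weeks have passed and Week 40 has not, the subject is treated and the visit schedule restarts. Inclusion criterion 3(d) likewise follows Week-36 rollovers to target or to a requested retreatment.

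The SAP's efficacy section is largely redacted. Its Section 10 drops the ITT and per-protocol populations and multiple imputation; its legible text does not mention the duration rule.

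**The concern.** Kaplan-Meier treats a censored subject as having the same remaining duration, on average, as those still at risk. A subject who leaves after Week 6 because symptoms need toxin or rescue has probably not got that prognosis. Censoring such subjects removes likely short responders from the risk set while crediting them with continuing effect.

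Route 3 raises a different problem. That subject neither reaches target nor withdraws, and once the schedule restarts the target for the earlier injection can no longer be observed cleanly. Without a rule, a programmer has to choose between censoring the cycle, counting it as an event, or running it on into the next cycle.

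At stake are the median duration and the proportion still in effect at each dose. If early exits are more common at some doses, the curves are distorted unequally.

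**Working it through.** **No plan figure to reproduce.** The documents state no expected median, withdrawal rate or early-retreatment rate. The sample size is a regulatory exposure count.

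**Direction, without assumptions.** At time t let n be at risk, d reach target and c exit for loss of benefit. The planned curve is multiplied by 1 − d/n. With exits counted as events the factor is 1 − (d + c)/n, which is never larger. So the recoded curve lies on or below the planned one, and the planned median cannot be the shorter of the two.

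**Direction against the protocol's own endpoint.** This depends on whether exit time is related to the subject's time to target, so both cases were simulated.

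**Assumed inputs (none from the documents).** Time to target Weibull, shape 2, true median 20 weeks; exits after Week 6; follow-up to 52 weeks; continuous time rather than the visit grid. All pre-target endings, including retreatment, are treated as censored in the planned analysis.

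*Dependent case: exit at 70–100% of the subject's own time to target*

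| Cycles affected | Censored (weeks) | Counted as events (weeks) | Gap | Censored minus true 20 |
|---|---|---|---|---|
| 5% | 20.4 | 19.8 | 0.6 | 0.4 |
| 10% | 20.8 | 19.7 | 1.1 | 0.8 |
| 20% | 21.7 | 19.3 | 2.4 | 1.7 |
| 30% | 22.9 | 19.0 | 3.9 | 2.9 |

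Simulation error is about 0.1 week. At 20%, the planned proportion still in effect at Week 24 is about 43%, against a true 37%.

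*Other settings.* With exits at 60–95% of own time to target, 5–30% affected and true medians of 16, 20 and 24 weeks, the gap between the two codings runs from 0.6 to 5.5 weeks.

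*Independent case: exit unrelated to time to target.* At true median 20 the planned median is 20.0. Counting exits as events gives 19.2, 18.3 and 17.6 with 6%, 11% and 17% of subjects affected. Here the plan is unbiased for the TWSTRS endpoint and the recoded version is the shorter one.

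**How much comes from each route.** In the 60–95% setting at 20% affected and median 20, the planned median is 21.8. Recoding only exits before 12 weeks gives 20.6; recoding all gives 18.9. So 1.2 of the 2.9 weeks comes from exits before 12 weeks. The other 1.7 comes from later endings: late rescue withdrawals, which are censored by rule, and pre-target retreatments, which have no legible rule.

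**Offset from zeros.** In that same setting, if 5% of subjects withdraw at or before Week 6 and are set to 0, the planned median falls from 21.8 to 21.0; with 10% it falls to 20.1, against a true 20.0.

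**The case against.** A reader might infer that the reported median is bound to be too long. The documents do not support that. The endpoint is a rating-scale threshold. Against it, censoring biases the median only if early exit predicts earlier crossing, and the independent case shows no bias. Some dependence is plausible, but its strength is unknown. The zero rule for withdrawals at or before Week 6 also pulls the median down, whatever the reason for leaving. It concerns different subjects, so it does not repair the later censoring, and any balance would be accidental. It does leave the net direction open.

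A reader might also infer that early-retreated cycles are excluded as events by rule. They are not: the legible text is silent, and the SAP pages where a duration rule would sit are redacted.

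A third inference would be that the main endpoint should itself become a composite. That changes the estimand by adding an open-label retreatment decision. In the dependent model the composite falls below the true TWSTRS median (19.0 to 19.8 against 20), and in the independent case further below.

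On weight: duration of effect is not a primary endpoint, efficacy is descriptive, and dose is selected by the investigator, so the by-dose curves are not a randomised comparison. Both withdrawal grounds are permissive, so few subjects may leave this way. All of this stands and limits the point. It does not remove the stated rule that censors loss-of-benefit withdrawals after Week 6 without regard to reason.

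**Conclusion.** The point holds in a limited form. After Week 6 and before target, withdrawal for needing toxin before 12 weeks or for needing rescue is censored by a stated rule, and that censoring is probably informative. It is certain that the planned median cannot be shorter than one counting these exits as events. Overstatement of the TWSTRS-defined median is conditional on early exit predicting earlier crossing, and may be offset by the zeros assigned at or before Week 6. Pre-target retreatment, including in Week-36 rollovers, is a gap in the legible text rather than a demonstrated error.

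The size is illustrative: under the dependent model, about half a week at 5% affected and 1 to 2.5 weeks at 10–20% between the two codings. Those figures assume that retreated cycles are censored too, and the legible censoring rule accounts for only part of them. This is worth correcting before analysis, but it does not touch the primary safety and immunogenicity conclusions.

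**What to change.** - Keep the TWSTRS-target definition as the main analysis.
- Add a prespecified sensitivity analysis, by dose, that counts a cycle as an event, dated at the visit where the need was recorded, when it ends before target through (i) withdrawal for needing toxin before 12 weeks, (ii) withdrawal for needing rescue, or (iii) retreatment before target.
- State how cycles ended by pre-target retreatment, including those of Week-36 rollovers, enter the main analysis, if the SAP does not already do so.
- Report the number of cycles censored by reason, dose and cycle, and alongside them the number set to 0 for withdrawal at or before Week 6.

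The cost is SAP wording and one extra derivation. Section 7.2 already requires the reason for discontinuation on the eCRF, SAP 7.1 already summarises reasons by cycle, and injection dates are inherent in the data. The team should confirm that the recorded reasons separate (i) and (ii) from other withdrawals. The downside is a second, shorter median in the report, which rests partly on an open-label retreatment decision. No clinical rule changes.
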